[figure not shown]
Does Negative Pressure Wound Therapy with Instillation Reduce the Bioburden of Infections?

Sponsor: KCI NCT04826965

Duke IRB#: Pro00105056

- **1) Protocol Title:** Does Negative Pressure Wound Therapy with Instillation Reduce the Bioburden of Infections?
- **2)** Purpose of the Study: The purpose of this study is to compare the microbiologic burden and need for further operative debridement of patients undergoing primary surgical debridement of infected tissue, soft tissue abscesses, or traumatic wounds, between patients treated with traditional VAC therapy and those treated with instillation with VAC Veraflo therapy with Cleanse Choice.

Primary endpoint: Bacterial bio-burden as measured by quantitative microbial PCR prior to debridement, immediately following initial debridement, after 2 days of VAC veraflo (or conventional VAC) therapy, and at the time of repeat operative debridements, if needed. We will use the MicroGen PCR platform (DBA Microgen Diagnostics, LLC, Lubbock, TX.) to report on the bacterial burden (reported on a log scale of bacteria per gram) present at the time of debridement.

Exploratory endpoint: Number of operative debridements required prior to reconstruction, number of days until final reconstruction, number of days until decision is made by surgeon that further debridements are no longer necessary, length of hospital stay, wound surface area.

3) Background & Significance:

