Plastic, orthopedic, vascular, and general surgeons commonly encounter infections. These may be post-traumatic (e.g. from a laceration while cooking or at the site of a fracture), embolic (seeding of infection from another source), or due to inoculation (e.g. from a contaminated needle used for intravenous illicit drug use). Regardless of the etiology, these patients present with complex problems that often require repeat debridement prior to reconstruction. Their hospital stays are lengthy, painful (in terms of pain from debridement and dressing changes), and expensive (based on the number of repeat operations required to debride infected tissue). The results of the initial surgical debridement are often uncertain- patient and disease factors contribute to the extent and recurrence of the disease and often surgeons will empirically schedule "second looks" to return to the operating room for a repeat debridement/inspection of the wound prior to performing a reconstruction, in order to avoid experiencing a failed reconstruction due to inadequate debridement. A possible cause for failure of reconstruction is the microbial bioburden present in the open wound. We hypothesize that the continuous irrigation as well as the cycles of wound/exudate disruption afforded by the V.A.C Veraflo technology with Cleanse Choice Dressing will reduce the microbial bioburden and possibly the need for operative debridement by allowing for around-the-clock non-excisional debridement and irrigation.

4) Design & Procedures:

Prospective randomized trial. Two arms, 20 patients in each arm. Study team expects to consent/enroll 60 patients in order to achieve 40 subject for evaluation due to voluntary opt-out, inability to return to OR for "second look" debridement on day 2, medical instability preventing further debridement, etc.

Day 0 - (Prior to surgery):

- Consent, randomization, enrollment

Day 1 (day of first operative debridement):

- Patient arrives in the operating room, anesthesia is induced. The extremity is prepared and draped in standard fashion.

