- Patients age 18 years or older who have an injury or infection for which surgical debridement (in the operating room) followed by VAC application is planned.
- Able to provide informed consent.

Page 4 of 7

- Speak and read English.
- Patients may be immunosuppressed, either through nature of disease or due to medication.
- Patients may be on systemic antibiotics or topical antimicrobials.
- Patients may present with exposed bone or joint space as part of either the debridement or traumatic injury.

Exclusion criteria:

- Patients on therapeutic anticoagulation to treat DVT/PE, atrial fibrillation, etc, for which we would include warfarin, therapeutic heparin or low-molecular-weight heparin, direct oral anticoagulants (e.g. rivaroxaban, dabigatran).
 - Most of these patients are on prophylactic anticoagulation to lower the risk of a DVT (e.g. heparin or enoxaparin subcutaneous injections). We would still like to include those patients in our study. These drugs are given to many hospitalized patients due to their immobility and are not prescribed to the same patients once they are safely living at home again. Additionally, many patients are on aspirin for the coronary prevention factor and we do not even usually hold this prior to surgery (even if someone wanted to, it takes days of waiting to reverse the platelet effects and these are acute wounds/infections). We would also like to include patients on aspirin or clopidogrel (anti-platelet agents), for example.
- 6) Subject Recruitment and Compensation: A maximum of 60 subjects will be consented in order to achieve 40 evaluable subjects. Duke subjects will be introduced by their healthcare team and if interested in participating, will be given more information by the research team. Potential subjects will be screened in the ED or Hospital and identified by an investigator or a member of the research team. An investigator will confirm eligibility criteria and a member of the site study team will notify the sponsor of a potential candidate for the study after the subject has been consented.

There is no subject compensation planned for this study.

7) Consent Process: Subjects will be introduced to the study by their physician and then the study team will provide additional information and consent if subjects are interested in participating in the study. See iRIS consent section for additional consent details. Patients will be approached after permission is granted by a member of the care team.

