Primary endpoint: Bacterial bio-burden as measured by quantitative microbial PCR prior to debridement, immediately following initial debridement, after 2 days of VAC veraflo (or conventional VAC) therapy, and at the time of repeat operative debridements, if needed. We will use the MicroGen PCR platform (DBA Microgen Diagnostics, LLC, Lubbock, TX.) to report on the bacterial burden (reported on a log scale of bacteria per gram) present at the time of debridement.

Exploratory endpoint: Number of operative debridements required prior to reconstruction, number of days until final reconstruction, number of days until

Page 6 of 7

decision is made by surgeon that further debridements are no longer necessary, length of hospital stay, wound surface area.

[name] to do analysis using JMP (SAS) software. Will use t-test for log scale of bacteria per gram.

Power analysis for a one-way ANOVA with 2 groups was conducted to determine a sufficient sample size using an alpha of 0.05, a power of 0.80, and a large effect size (f = 0.40) Based on the aforementioned assumptions, the desired sample size is 25.52. Original funding called for 60 patients, but funding agency subsequently retracted their offer to cover indirect costs, so the sample size was decreased to 40 patients total as the grant now must absorb the indirect costs.

13) Data & Safety Monitoring:

All adverse events related to the study will be signed off on by the PI and reported to the IRB in accordance with Duke and HIPAA policies.

Privacy, Data Storage & Confidentiality: Any data that is stored in paper or non-digital format will be locked in a file cabinet within a controlled access office. The office will be locked when not in use by the study team. All electronic study information will be stored on the secure Surgery Server in the IRB folder for this study with access limited only to the study team. All study information will be stored in accordance with the RDSP for this study.

Confidentiality of subject data will be ensured by de-identification of subject data. During data collection, subject identifiers and relevant data elements will be recorded in the database. Then, study-specific identification numbers will be assigned to each subject. Prior to dissemination of any information in this database beyond the DUMC's secure servers or firewall, all identifiers will be stripped from the database and data will only be referenced by the study-specific identification numbers.

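### Infected and uninfected wounds are pooled with no stated stratification and an unadjusted t-test, which costs precision if burden differs by wound type; the title names only infections

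*Combined protocol and SAP*

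**What the plan says.** The title asks "Does Negative Pressure Wound Therapy with Instillation Reduce the Bioburden of Infections". Section 2 (Purpose of the Study) is wider and covers patients undergoing "primary surgical debridement of infected tissue, soft tissue abscesses, or traumatic wounds". The inclusion criteria in section 5 follow the purpose: they admit "Patients age 18 years or older who have an injury or infection for which surgical debridement (in the operating room) followed by VAC" is planned. Neither a confirmed infection nor a minimum burden is required.

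On allocation, section 4 says "Prospective randomized trial. Two arms, 20 patients in each arm". It gives no randomisation method, blocking or stratification factor. On analysis, section 12 says "Will use t-test for log scale of bacteria per gram". It does not name a specimen for the test, a covariate or an infected-wound estimate. The same section sizes the trial by a two-group ANOVA with alpha 0.05, power 0.80 and f = 0.40, and states that "the desired sample size is 25.52". Funding then changed, "so the sample size was decreased to 40 patients total as the grant now must absorb the indirect costs".

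Some material for a better analysis is already collected. Specimens 1 and 2 are taken before the dressing goes on (section 4, Day 1), and the data list in section 4 includes type and mechanism of injury. That list has no item for whether the wound is infected at entry.

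**The concern.** Two points meet here. First, a reader who takes the title at its word expects an estimate in infected wounds, and the plan gives only a pooled one.

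Second, wound type may well be prognostic for bacterial burden. If it is, a plain t-test leaves the between-type variation in the error term, and with 20 per arm an uneven split of wound types can move the one estimate the trial will produce. The trial has little power to spare, because 40 patients is fewer than its own calculation asks for (see the working). The baseline measurements that would recover precision are taken but have no stated role in the analysis.

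**Working it through.** **Inputs.** From section 12: alpha 0.05 and f = 0.40, so d = 2f = 0.80 for two groups. From section 4: 20 per arm. Assumed, because the documents give no figures: half the wounds infected, a mean gap of g = 1 or 2 within-type SD between wound types, and d = 0.8 in units of the within-type SD in both types.

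**1. The plan's own figure.** The noncentrality is n·d²/2 with 1 and 2n − 2 degrees of freedom. Solving for power 0.80 gives n = 25.52. The stated figure therefore reproduces, but per group: 26 per group, 52 in total. Read as a total it gives power of about 0.49. At n = 20 the noncentrality is 20 × 0.64/2 = 6.4 and power is 0.69.

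**2. Cost of ignoring wound type.** With half the wounds of each type, the variance seen by the t-test is 1 + 0.25g².

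| Gap g | Pooled SD | 0.8 / pooled SD | Power, plain t-test |
|---|---|---|---|
| 0 | 1.000 | 0.800 | 0.69 |
| 1 | √1.25 = 1.118 | 0.716 | 0.60 |
| 2 | √2.00 = 1.414 | 0.566 | 0.41 |

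Simulation (6,000 runs per setting) agrees: 0.596 and 0.414. With a wound-type term, simulated power under simple randomisation is 0.673 (1 SD gap) and 0.687 (2 SD gap), about 0.68 in both. If there is no gap, the term costs about 0.01 of power (0.69 to 0.68).

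**3. Chance imbalance.** With 20 infected wounds among 40 and 20 per arm (hypergeometric), and shift = g × difference in proportions:

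| Split of infected wounds | Difference | Probability of this or worse | Shift, g = 1 | Shift, g = 2 |
|---|---|---|---|---|
| 12 v 8 | 20 points | 0.343 | 0.2 SD | 0.4 SD |
| 13 v 7 | 30 points | 0.113 | 0.3 SD | 0.6 SD |
| 14 v 6 | 40 points | 0.026 | 0.4 SD | 0.8 SD |

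If the total infected is left random (independent binomials), the first two probabilities are 0.27 and 0.08. The planned effect for comparison is 0.8 SD.

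**4. Validity of the test.** With no treatment effect and a 2 SD gap, the simulated type I error of the t-test under simple randomisation is 0.049. As an extreme case, let wound type be the only source of variation. A 12 v 8 split then gives t = 1.26 (p = 0.22), and 13 v 7 gives t = 1.94 (p = 0.06). Only 14 v 6 or worse reaches significance by imbalance alone. The result does not depend on g, because shift and SD scale together.

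**5. Stratifying without adjusting.** With a 2 SD gap, stratified allocation followed by a plain t-test gives type I error 0.006 and power 0.36. With the stratum in the model the figures are 0.052 and 0.70. The gain comes from the model term.

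**6. Infected wounds alone.** With about 10 per arm, power for d = 0.8 is 0.40. The 95% half-width is 2.101 × √(2/10) = 0.94 SD.

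**The case against.** Three stronger readings are tempting, and the documents support none of them.

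*That the trial enrols patients outside its question.* The purpose names traumatic wounds and eligibility matches it. A pooled estimate answers the purpose as written. The fault is a title narrower than the purpose.

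*That uninfected wounds dilute the effect.* If half the wounds gained nothing, d would fall to 0.8 × 0.5 = 0.40 and power to 0.23; with a quarter, d = 0.60 and power 0.46. This needs an assumed share of uninfected wounds, no effect in them, and f = 0.40 to be an effect in infections only. The documents give none of these. Both arms are debrided before the dressing is applied, so room to fall depends on the burden left or regrown afterwards, which is not reported by wound type. Dilution is possible but not shown.

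*That imbalance could produce a positive result on its own.* Randomisation protects the error rate, and imbalance alone reaches significance only at a 40-point split, probability 2.6%.

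There are also fair objections to the remedy. Section 3 allows infections to be post-traumatic, so infection against trauma is not a clean division without a rule. Up to 60 patients are consented, with randomisation on Day 0, to reach 40 evaluable, so balance within strata may not carry through to the analysed set. Adjusting for specimen 1 or 2 needs no wound-type definition at all. These points stand. They are reasons to define the stratum in one line and to put both stratum and baseline burden in the model, not to leave the t-test unadjusted.

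**Conclusion.** The point holds as one of precision and labelling. The title is narrower than the purpose and eligibility, allocation has no stated stratification, and the planned test uses neither wound type nor the burden measured before the dressing.

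Under the stated assumptions, the plain t-test gives up about 0.08 of power at a 1 SD gap (0.68 − 0.60) and 0.27 at a 2 SD gap (0.68 − 0.41). If there is no gap, nothing is lost by the plan and the adjustment costs about 0.01. A chance imbalance of 20 points or more, with probability about one in three, would move the realised estimate by a quarter (0.2/0.8) to a half (0.4/0.8) of the planned effect or more. The comparison remains valid on average. How far precision suffers in practice depends on the wound mix and the gap in burden, which the documents do not give.

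**What to change.** 1. Before randomisation, record one field: clinically infected wound (post-traumatic infections count as infected) or uninfected acute traumatic wound.
2. Stratify the randomisation on that field with blocked lists, and state the method in section 4.
3. In section 12, replace the t-test with a linear model (ANCOVA) for log bacteria per gram at specimen 3, with arm, wound-type stratum and pre-dressing log burden. Name specimen 1 or specimen 2 as the covariate in advance. Do not stratify and then keep the plain t-test.
4. Label the pooled estimate as applying to infected and traumatic wounds, and align the title with the purpose and eligibility.
5. Report the arm difference in infected wounds with its interval as supportive, stating that its precision is low.

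The cost is one data field, two randomisation lists in place of one, and one or two degrees of freedom. No extra patients, specimens or procedures are needed.

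### The primary endpoint spans every sampling occasion, and the planned t-test does not say which specimen, or whether a raw value or a change, is compared between the arms

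*Combined protocol and SAP*

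**What the plan says.** The endpoint is stated in the same terms in section 2 ("Primary endpoint: Bacterial bio-burden as measured by quantitative microbial PCR prior to debridement" and onwards) and in section 12. It lists four kinds of occasion. The first three are "Bacterial bio-burden as measured by quantitative microbial PCR prior to debridement, immediately following initial debridement, after 2 days of VAC veraflo" in one arm, with the conventional device in the other, and the fourth is "and at the time of repeat operative debridements, if needed".

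Section 12 gives one sentence of analysis: "Will use t-test for log scale of bacteria per gram". No section names a primary occasion, a change score, a covariate, a way of combining repeated values or a multiplicity rule.

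The sample size paragraph of section 12 reads "Power analysis for a one-way ANOVA with 2 groups was conducted", and its inputs are given as "using an alpha of 0.05, a power of 0.80, and a large effect size (f = 0.40"). It does not say to which measurement f refers.

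Section 4 gives the sequence:

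- Day 0: "Consent, randomization, enrollment".
- First operation: specimen 1 at the start and specimen 2 at the end of debridement; the randomised dressing is then applied.
- Second operation: specimen 3 at the start. What follows is left to the surgeon.
- Third and later operations: a specimen at the start of each. The step is described as optional and as unnecessary for many patients.

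**The concern.** A two-sample t-test takes one value per patient, but this endpoint supplies at least three. The analysis cannot be run until someone makes a choice that the plan leaves open, and nothing prevents that choice from being made after the data are seen.

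The listed occasions are also not interchangeable. The first two come before any exposure to the randomised device. The last kind exists only for patients selected by a decision taken after randomisation, and the number of debridements is itself an exploratory endpoint. Only specimen 3 is both taken after the device and planned for every evaluable patient. Even there, the raw value, the change from specimen 1 and the change from specimen 2 are three different tests with different power.

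**Working it through.** **Inputs from the documents.** 20 evaluable patients per arm (section 4); alpha 0.05, power 0.80, f = 0.40, stated sample size 25.52 (section 12).

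**Assumptions, because the documents give no figures.** Normal data, equal SD at each specimen, equal correlation r of 0, 0.3, 0.5 or 0.7 between specimens, two-sided tests.

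**Step 1: the plan's own figure.** For two equal groups d = 2f = 0.80. A two-sided two-sample t-test with 80% power then needs 25.52 per arm (noncentral t), or 51.05 in total. The stated 25.52 is therefore reproduced as a per-arm figure for a single two-group comparison of one value per patient.

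**Step 2: false positives at specimen 3.** Simulated trials with no device effect, 100,000 per setting, 20 per arm, each test at 0.05. The entry is the chance of at least one significant result.

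| Contrasts available | r = 0 | 0.3 | 0.5 | 0.7 |
|---|---|---|---|---|
| Raw, change from specimen 1, change from specimen 2 | 0.114 | 0.122 | 0.127 | 0.129 |
| Raw, change from specimen 2 | 0.083 | 0.089 | 0.092 | 0.093 |
| ANCOVA alone | 0.051 | 0.051 | 0.051 | 0.050 |

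**Step 3: power if f = 0.40 applies to the raw specimen 3 value.**

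- Raw t-test: noncentrality 0.80 × √(20/2) = 2.53 on 38 df, power 69%.
- Change from specimen 2: the SD of the change is √(2(1 − r)), so the effective d is 0.80/√(2(1 − r)) = 0.57, 0.68, 0.80, 1.03.
- ANCOVA: the residual SD is √(1 − r²), so the effective d is about 0.80/√(1 − r²) = 0.80, 0.84, 0.92, 1.12. The power below is simulated, which allows for the lost degree of freedom.

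| Test | r = 0 | 0.3 | 0.5 | 0.7 |
|---|---|---|---|---|
| Raw t-test | 69% | 69% | 69% | 69% |
| Change t-test | 41% | 55% | 69% | 89% |
| ANCOVA | 68% | 72% | 80% | 92% |
| Raw and change disagree on significance | 34% | 31% | 29% | 30% |

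**Step 4: power if f = 0.40 applies to the change from specimen 2.** The change test then has 69% throughout. The effective d of the raw test is 0.80 × √(2(1 − r)) = 1.13, 0.95, 0.80, 0.62, with power 94%, 83%, 69% and 48%. The ranking of the two t-tests on either side of r = 0.5 does not depend on where f applies; the level of power does.

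**Step 5: why ANCOVA is the safer choice.** Relative to the raw variance of 1, its residual variance is 1 − r² = (1 − r)(1 + r). This never exceeds 1 and, since 1 + r ≤ 2, never exceeds the change-score variance 2(1 − r). Under the equal-variance assumption this holds wherever f applies.

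**Step 6: late specimens.** The documents give no rate of third operations by arm and no link between burden and return to surgery. No size or direction can be calculated for the selection.

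**The case against.** The best defence is that the intended analysis is clear enough. Section 4 lists, among the reasons for consenting 60 to obtain 40, inability to return for a second look "debridement on day 2, medical instability preventing further debridement", which ties evaluability to specimen 3. The power calculation assumes one two-group comparison. Section 2 speaks of comparing burden between treatments, and the test is on a level of bacteria, not a change. All of this stands, and it points to the raw specimen 3 value. It remains an inference: the title and the hypothesis in section 3 are worded as a reduction, which can be read as a change, and the endpoint itself still includes the later operations.

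A reader might infer more than the documents support:

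- *That t-tests are planned at specimens 1 and 2.* The text lists measurement occasions, not comparisons, and listing them is consistent with use as baselines.
- *That raw and change tests could reach opposite conclusions.* They can differ on crossing 0.05. In 40,000 simulated trials per setting at d = 0.80, none was significant in opposite directions. Part of the disagreement at r = 0 is simply unequal power.
- *That testing specimen 3 and one late occasion carries an error of 0.08 to 0.10.* That figure needs all 20 per arm to give a late specimen, while section 4 expects many patients not to have further debridement.

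It is also fair to say that ANCOVA replaces a valid test, that its gain depends on an unknown correlation, and that successive samples may come from different sites or tissue types (section 4 records both), which could lower that correlation.

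**Conclusion.** The point holds. The trial's only primary endpoint includes occasions that cannot form a randomised comparison of the device, and its only test does not identify the value compared. At the one suitable occasion, leaving the contrast open raises the false-positive chance from 0.05 to about 0.11 to 0.13 with three contrasts, or 0.08 to 0.09 with two. If f = 0.40 applies to the raw value, the conclusion on significance would depend on the unstated choice in about three trials in ten. These figures rest on normal data, equal variances and assumed correlations of 0 to 0.7, and the error rates describe what happens if the choice is made on the results. The documents do not suggest that anyone intends this. Selection among late specimens is a real threat to that comparison, but its size and direction are unknown.

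**What to change.** In sections 2 and 12, name one primary comparison: log bacteria per gram at specimen 3, between randomised arms, two-sided 0.05, by ANCOVA with specimen 2 (the last sample before the device) as covariate. If the planned t-test is kept, state that it is on the raw specimen 3 value.

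Report specimens 1 and 2 by arm as baselines. Report specimens from third and later operations descriptively, with the proportion of each arm contributing and no confirmatory p-value.

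A sensitivity analysis with specimen 1 as covariate is optional. Both specimens follow Day 0 randomisation, but specimen 1 precedes the first debridement, and the plan does not say when the surgeon learns the allocation.

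When naming the occasion, reconcile the two descriptions of it: the endpoint refers to two days of therapy, whereas section 4 runs therapy from Day 1 to Day 2.

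**Cost.** Wording only; no change to sampling or patient numbers. Later occasions lose primary status. ANCOVA spends one degree of freedom (about 1 point of power if the correlation is 0) and needs specimen 2 for every analysed patient.

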- A small piece of tissue (on the order of grams) is excisionally debrided in standard surgical fashion. This tissue **specimen 1** is placed into the plastic specimen collection cup provided by MicroGen, labeled, and the plastic bag containing the cup is sealed. The cardboard box provided in the kit is sealed and, being pre-addressed and pre-paid, is sent to MicroGen in Texas. **The patient receives a random number for use with the MicroGen sample and no identifying information (Name, age, MRN) is sent to MicroGen.**
- Debridement proceeds in standard surgical practice. The prior specimen collection does not rob the lab of tissue that the surgeon, in his/her judgment seeks to send for microbiology culture or pathology.
- At the conclusion of debridement/irrigation, a repeat small piece of tissue **specimen 2** is excised and sent to MicroGen in the same manner.
- At the conclusion of debridement, based on randomization, a wound vac or wound vac with cleanse choice dressing, track pad duo, and saline irrigation is applied. The wound is dressed in standard fashion according to the sugeon's preference (e.g. splint, ACE wrap, etc.).
- Patient emerges from anesthesia, and heads to recovery/floor or ICU as planned.

Day 1 until day 2:

- Negative pressure wound therapy or negative pressure wound therapy with irrigation proceeds automatically, 24/7

Day 2 (second operative debridement):

- Patient arrives in the operating room, anesthesia is induced. The extremity is prepared and draped in standard fashion.
- A small piece of tissue (on the order of grams) is excisionally debrided in standard surgical fashion. This tissue **specimen 3** is placed into the plastic specimen collection cup provided by MicroGen, labeled, and the plastic bag containing the cup is sealed. The cardboard box provided in the kit is sealed and, being pre-addressed and pre-paid, is sent to MicroGen in Texas. **The patient receives a random number for use with the MicroGen sample and no identifying information (Name, age, MRN) is sent to MicroGen.**
- Debridement proceeds in standard surgical practice. The prior specimen collection does not rob the lab of tissue that the surgeon, in his/her judgment seeks to send for microbiology culture or pathology.

- This next step is completely up to the surgeon. Additional debridement, reconstruction, fracture fixation, reconstruction, closure, repeat wound vac. Additional samples are not collected.

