- Patient emerges from anesthesia, and heads to recovery/floor or ICU as planned.

Future debridements, if performed:

- Done at Day 5 (+/- 1 day). This is an optional step as many patients will not require additional debridement. Tissue samples will be sent at the time of the third surgery, whether it is a debridement, reconstruction, or other procedure.
- Tissue collection at the start of each further surgery for MicroGenPCR. In the event that wounds are dirty/infected and require repetitive debridements, we may collect as many as n additional samples for n additional operative debridements to track the bioburden over time.

Demographics and data to be collected on participants:

Patient name, age, gender, MRN, height, weight, type of injury, mechanism of injury, concurrent fracture involved with the wound, major vascular injury, prior debridements before presentation, date/time of injury, date/time of ED or hospital presentation, date/time of irrigation in ED (if performed), date/time of preliminary surgery, date/time of additional debridements, reconstructions, number of days until closure/reconstruction, number of days to decision is made that debridement is complete, comorbidities: [diabetes, smoking, steroid use, radiation], lab values: [CBC, BMP, albumin], vital signs. Surgical details: type of anesthesia, surgeon, surgical service, operative time, anesthesia time, type of debridement, level of debridement, whether a concurrent operation was performed, wound area/area of debridement, whether a drain was placed, volume of irrigation, pre-op intra-op and post-op antibiotics. Type of tissue debrided and sent for our samples (and location within the wound). If debridement is abandoned, e.g. if surgeon decides only an amputation will cure this wound.

ICU stay, blood transfusion, mechanical ventilation postoperatively. Date of discharge. Several of these variables, including when the decision is made to reconstruct, may require searching the EMR after discharge. For example, a patient may be sent home with a plan for a nurse to change dressings for weeks at home. The patient may present to clinic after discharge and the surgeon examines the wound then decides to schedule wound closure/reconstruction (e.g. skin graft, flap, etc).

We will follow the patients for the duration of care.

5) Selection of Subjects:

Inclusion criteria:

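### If Section 12 means a t-test at specimen 3, adjusting for the specimen 1 burden already collected is a cheap improvement (not the repair of an error) that gains power once their correlation exceeds about 0.17

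*Combined protocol and SAP*

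**What the plan says.** Section 12 (Data Analysis & Statistical Considerations) has one sentence of analysis: "Will use t-test for log scale of bacteria per gram". It names no specimen, covariate, change score or sidedness. The endpoint above it covers several times: "Bacterial bio-burden as measured by quantitative microbial PCR prior to debridement, immediately following initial debridement, after 2 days of VAC veraflo" therapy, or conventional VAC, and then any repeat operative debridement. The sample size in the same section comes from a two-group one-way ANOVA without a covariate.

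Section 4 (Design & Procedures) gives the order of events:

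- Day 0, before surgery: "Consent, randomization, enrollment".
- Start of the first operation, specimen 1: "A small piece of tissue (on the order of grams) is excisionally debrided in standard surgical fashion".
- After that debridement, specimen 2: "At the conclusion of debridement/irrigation, a repeat small piece of tissue".
- Then the allocated device: "At the conclusion of debridement, based on randomization, a wound vac or wound vac with cleanse choice dressing".
- Start of the second operative debridement, specimen 3, collected and sent in the same way as specimen 1.

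The list of data to be collected includes "prior debridements before presentation" and any irrigation in the emergency department. Specimen 1 is therefore a pre-device baseline, but not always a sample from an untreated wound. The same list records "Type of tissue debrided and sent for our samples (and location within the wound".

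**The concern.** The specimen 1 burden is measured in the same units as the outcome and before the device can act on it. Nothing in the plan uses it as a covariate. If patients who start with a high burden tend to finish with a high burden, an unadjusted comparison carries between-patient variation that the model could remove at no cost in patients or samples.

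What is at stake is precision. Section 12 says that the trial was reduced to 40 patients when the funder withdrew cover for indirect costs. Extra patients are therefore hard to obtain, while a covariate already being collected is not.

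**Working it through.** **Inputs.** From the documents: 20 evaluable patients per arm (Section 4); alpha 0.05, power 0.80 and f = 0.40 (Section 12). For two equal groups d = 2f = 0.80 SD. Assumed: two-sided testing (supported by step 1), normal log burden with a common slope, SD at specimen 3 set to 1, and a correlation r between specimens 1 and 3 of 0 to 0.7. The documents give neither the SD nor r.

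**1. The plan's own figure.** For a two-sample t-test with n per group, the noncentrality is d·√(n/2) on 2n − 2 df. Solving for 80% power at two-sided 5% gives n = 25.52 per group, which matches the stated 25.52. One-sided testing would give 20.03. Read as a total, 25.52 would give only 49% power. The figure is therefore per group and two-sided.

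**2. t-test at specimen 3, 20 per arm.** Noncentrality 0.80 × √10 = 2.530 on 38 df gives **69.3%** power.

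**3. ANCOVA of specimen 3 on arm and specimen 1.** The noncentrality is 2.530 / √[(1 − r²)(1 + 1/(2n − 4))], with 1/(2n − 4) = 1/36, on 2n − 3 = 37 df. The factor 1 + 1/36 allows for chance baseline imbalance. Half-widths are critical t × standard error, with critical t = 2.024 (38 df) or 2.026 (37 df). For the t-test this is 2.024 × √(2/20) = 0.64 SD.

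| r | Noncentrality | ANCOVA power | Gain over 69.3% | 95% CI half-width (SD) |
|---|---|---|---|---|
| 0 | 2.495 | 68.1% | −1.2 | 0.65 |
| 0.3 | 2.616 | 72.2% | +2.9 | 0.62 |
| 0.5 | 2.881 | 80.1% | +10.8 | 0.56 |
| 0.7 | 3.494 | 92.5% | +23.2 | 0.46 |

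The two tests have equal power at r = 0.169. Integrating exactly over the baseline imbalance gives 0.167, so about 0.17 either way. Power of 80% needs r of about 0.50. Simulation with 200,000 trials per setting gave ANCOVA against t-test of 68.1% v 69.4% at r = 0, 72.1% v 69.3% at 0.3, and 80.2% v 69.4% at 0.5.

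**4. If the sentence means change from specimen 1.** With equal SDs the noncentrality is 2.530 / √[2(1 − r)] on 38 df. Power is 41%, 55%, 69% and 89% at r = 0, 0.3, 0.5 and 0.7, below ANCOVA at each. If d = 0.80 was meant in SDs of the change, that t-test has 69.3% at any r, and ANCOVA has 93.0%, 85.4%, 80.1% and 75.0%. With unequal SDs (ratio of specimen 1 to specimen 3 from 0.5 to 2), the change score leads ANCOVA by at most 1.1 points.

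**5. Missing specimen 1.** With one baseline per arm missing at random and replaced by the mean over both arms, simulated power is 68.2%, 72.0%, 79.6% and 91.2% at the same r, and break-even stays at about 0.17. With two per arm, break-even is about 0.18. Type I error was 4.97% to 5.04%. Dropping those patients instead would move break-even to 0.29 (one per arm) or 0.37 (two per arm).

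**The case against.** The strongest objection is that nothing here is wrong and the benefit is unknown. Between randomised arms the t-test is valid, and the gain depends wholly on an r that no section reports. The protocol gives reasons to expect a low value: one small piece of tissue per specimen, varying tissue type and location, and a debridement between specimens 1 and 3. At r = 0.3 the gain is 2.9 points and the half-width falls only from 0.64 to 0.62 SD. All of this stands. It limits the point to an improvement of unknown size but does not remove it, because the worst loss is about 1.2 points.

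A second objection is that the 0.17 threshold applies only if the sentence means specimen 3. That also stands. A change from specimen 2 is not excluded by the wording, and no claim is made about it.

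A third is that the unnamed time point matters more than the covariate. It is a separate decision, and it limits what can be said for the t-test. If specimens 1, 2 and 3 were each tested at 5%, the chance of at least one false positive would be about 11% to 14% at correlations from 0.7 down to 0 (1 − 0.95³ = 14.3% at 0). The 5% level is secure only for one pre-named specimen.

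Loss of specimen 3, when a patient does not return for the second look, affects both analyses alike and does not favour the t-test.

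**Conclusion.** The point holds as a cheap improvement. If the planned test is a t-test at specimen 3, adjusting for specimen 1 changes power from 69.3% to between 68.1% and 92.5% over r = 0 to 0.7, with a gain above about 0.17. If the planned test is change from specimen 1 with equal SDs, ANCOVA has more power across the same range. These figures rest on 20 evaluable per arm, d = 0.80, two-sided 5%, approximate normality on the log scale, and assumed values of r.

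A reader might infer that omitting the baseline biases the comparison or invalidates the t-test. The documents do not support that: allocation is randomised, and the t-test's interval already allows for chance baseline differences. A reader might also infer that adjustment restores the planned 80% power. That needs r of about 0.50, and nothing in the documents shows that r is so high.

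**What to change.** Replace the analysis sentence in Section 12 with:

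> The primary analysis is an ANCOVA of log bacteria per gram at specimen 3 (taken at the start of the second operative debridement) on treatment arm, adjusting for log bacteria per gram at specimen 1. A missing specimen 1 is replaced by its mean over both arms. The adjusted mean difference is reported with its 95% CI. Other specimens are secondary. The unadjusted t-test at specimen 3 and the model adjusting for specimen 2 are sensitivity analyses.

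Two matters are for the investigators:

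- They must confirm specimen 3 as the single primary time point.
- They must reconcile the length of therapy before specimen 3. The endpoint in Sections 2 and 12 puts it at two days, while Section 4 applies the device on Day 1 and takes the specimen on Day 2. The proposed text identifies the specimen by its operation so that it does not settle this.

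Preferring specimen 1 to specimen 2 as the main covariate is a judgement. Both follow Day 0 randomisation, but specimen 2 also follows the study debridement, and no blinding of the surgeon is described.

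The cost is a few sentences and one degree of freedom, about 1.2 points of power if r = 0. Specimens 1 to 3 are already planned, and JMP, the software named in Section 12, fits the model.
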